# 5.6 Participant Evaluability

If pre-operative VB-111/placebo is not able to be given to a participant or a participant did not undergo the scheduled surgical resection for any reason, then the participant will be unevaluable for the primary efficacy analysis. Additional patients will be recruited to the trail until 15 evaluable patients in each arm.

# 5.7 General Concomitant Medication and Supportive Care Guidelines

Therapies, medications or vaccinations specifically prohibited in the exclusion criteria (Section 3.2) are not allowed during the ongoing trial except as outlined below. If there is a clinical indication for one of these or other medications or vaccinations specifically prohibited during the trial, discontinuation from trial therapy may be required. The Investigator should discuss any questions regarding this with the Overall Principle Investigator, [name], or his designee. The final decision on any supportive therapy or vaccination rests with the Overall Principle Investigator.

### 5.7.1 Acceptable Concomitant Medications

All treatments that the investigator considers necessary for a participant's welfare may be administered at the discretion of the investigator in keeping with the community standards of medical care.

All concomitant medication will be recorded on the case report form (CRF) including all prescription, over-the-counter (OTC), herbal supplements, and IV medications and fluids. If changes occur during the trial period, documentation of drug dosage, frequency, route, and date may also be included on the CRF, when information is available.

All concomitant medications received from date of consent up to 30 days after the last dose of trial treatment should be recorded. Concomitant medications administered after 30 days after the last dose of trial treatment should be recorded for SAEs.

# 5.7.2 VB-111 Prophylactic Requirements

To avoid fever following study drug VB-111 administration, all patients will receive 900-1000 mg of acetaminophen starting approximately 1-2 hours prior to VB-111/Placebo dosing followed by 450-500 mg when necessary for up to approximately 36 hours. Prophylaxis of Dexamethasone 4 mg before VB-111/Placebo dosing followed by 4 mg for 3 days may be given if deemed necessary by the investigator.

# 5.7.3 Prohibited Concomitant Medications

Participants are prohibited from receiving the following therapies during the Screening and Treatment Phase of this trial:

- Anti-cancer systemic chemotherapy or biological therapy (bevacizumab or biosimilar can be used to control effects of edema and mass effect. A washout period of 2 weeks between each VB-111 and bevacizumab or biosimilar dose is recommended)
- Immunotherapy not specified in this protocol
- Chemotherapy not specified in this protocol
- Investigational agents other than VB-111
- Radiation therapy
- Systemic glucocorticoids for any purpose other than to modulate symptoms from an adverse event of suspected immunologic etiology or to control cerebral edema. The use of physiologic doses of corticosteroids may be approved after consultation with the Overall Principal Investigator.

Participants who, in the assessment by the treating investigator, require the use of any of the aforementioned treatments for clinical management should be removed from the trial. Participants may receive other medications that the treating investigator deems to be medically necessary.

The Exclusion Criteria describes other medications which are prohibited in this trial unless otherwise described (e.g. bevacizumab or biosimilar and Group C study treatment). There are no prohibited therapies during the Post-Treatment Follow-up Phase.

### 5.7.4 Tumor Treating Fields (TTF)

TFF should not be given from randomization until surgery and after surgery only in Group C. TTF should not be given at any point for Group A and Group B after randomization.

#### 5.7.5 Cerebral Edema

Due to the immunologic nature of VB-111, cerebral edema may theoretically result due to immune infiltration of the brain. Symptoms related to cerebral edema may include headache or neurologic deficit that is either new or worsened. Participants with any signs or symptoms of cerebral edema should be treated as clinically appropriate, including initiation or increased systemic corticosteroid dosing, initiation of bevacizumab or biosimilar, treatment with an osmotic diuretic, or surgical decompression.

Bevacizumab or biosimilar may be used to control edema, mass effect, or as a steroid-sparing agent for as long as the treating investigator deems clinically necessary. Treatment with additional VB-111 may be re-initiated if clinically significant symptoms attributable to cerebral edema have resolved to grade  $\leq 1$  or pre-treatment baseline or after discussion with the Overall Principal Investigator. A washout period of 2 weeks between VB-111 and bevacizumab or biosimilar doses is recommended. Participants who develop CTCAE 5.0 grade 4 cerebral edema attributable to VB-111 should not receive further doses and should discontinue study therapy.

### 5.7.6 Diet/Activity/Other Considerations

### 5.7.6.1 Diet

Participants should maintain a normal diet unless modifications are required to manage an AE such as diarrhea, nausea or vomiting.

# 5.7.6.2 Contraception

Eligible female patients will be informed of special restrictions with regards to pregnancy and breast-feeding throughout the study period. Both men and women should not attempt pregnancy and women should not be pregnant or breast-feeding while participating in this study. If sexually active, women of childbearing potential and men with female spouses of childbearing potential must agree to use two methods of reliable contraception simultaneously or to practice complete abstinence from heterosexual contact. One method must include a highly effective method such as an intrauterine device, hormonal (birth control pills, injections or implants), tubal ligation or partner's vasectomy and one can be an additional (barrier method such as a male condom, diaphragm or cervical cap or hormonal) prior to study entry, while receiving treatment and for 120 after undergoing treatment. If there is any question that a participant will not reliably comply with the requirements for contraception, that participant should not be entered into the study.

#### 5.7.6.3 Use in Pregnancy

If a participant inadvertently becomes pregnant while on treatment with the study agent in this clinical trial, the participant will immediately be removed from the study. The site will contact the Overall Principal Investigator and VBL within 1 working day of investigator learning of the pregnancy. The site will contact the participant at least monthly and document the participant's status until the pregnancy has been completed or terminated. The outcome of the pregnancy will be reported to the Overall Principal Investigator and to VBL without delay and within 1 working day if the outcome is a serious adverse experience (e.g., death, abortion, congenital anomaly, or other disabling or life-threatening complication to the mother or newborn).

1. The study investigator will make every effort to obtain permission to follow the outcome of the pregnancy and report the condition of the fetus or newborn to the Overall Principal Investigator and VBL. If a male participant impregnates his female partner the study personnel at the site must be informed immediately and the pregnancy reported to the Overall Principal Investigator and VBL. Scan and email documents to NeuroOnc\[contact] and [contact] with the subject title as "VB-111 Pregnancy."

### 5.7.6.4 Use in Nursing Women

It is unknown whether VB-111 is excreted in human milk. Since many drugs are excreted in human milk and because of the potential for serious adverse reactions in the nursing infant, participants who are breast-feeding are not eligible for enrollment.

#### 5.8 Duration of Therapy and Criteria for Removal from Study Treatment

Duration of therapy will depend on individual response, evidence of disease progression and tolerance. Treatment may continue for up to 24 months or until one of the following criteria applies:

- The participant or legal representative (such as a parent or legal guardian) withdraws consent
- Radiographic tumor progression is supported by two consecutive time points of tumor growth

*Note:* For unconfirmed radiographic disease progression, please see Section 10.4

*Note:* A participant may be granted an exception to continue on treatment with confirmed radiographic progression if clinically stable or clinically improved, please see Section 10.4.

- Unacceptable adverse event(s)
- Intercurrent illness that prevents further administration of treatment
- Investigator's decision to withdraw the participant
- The participant has a confirmed positive serum pregnancy test
- Noncompliance with trial treatment or procedure requirements
- General or specific changes in the participant's condition render the participant unacceptable for further treatment in the judgment of the treating Investigator
- Administrative reasons.

Participants will be removed from the protocol therapy when any of these criteria apply. The reason for removal from protocol therapy and the date the participant was removed must be documented in the case report form (CRF). Alternative care options will be discussed with the participant.

When a participant is removed from protocol therapy and/or is off of the study, the participant's status must be updated in OnCore in accordance with REGIST-OP-1.

In the event of unusual or life-threatening complications, treating Investigators must immediately notify the Overall Principal Investigator.

# 5.9 End of Treatment Evaluation and Follow-Up

The End of Treatment and Follow-up visit procedures are listed in Section 10 (Study Calendar). After the end of treatment, each participant will be followed for 30 days for adverse event monitoring and 90 days for SAE monitoring.

Participants removed from protocol therapy for unacceptable adverse events will be followed until resolution or stabilization of the adverse event.

Participants who discontinue for reasons other than progressive disease will have post-treatment follow-up for disease status until disease progression, withdrawing consent or becoming lost to follow-up.

# 5.10 Long-Term Follow-Up and Study Completion

After documented disease second progression, each participant will be followed by telephone or medical record review for overall survival until they meet criteria for removal from study as detailed below.

Participants will be removed from study when any of the following criteria apply:

- Lost to follow-up
- Withdrawal of consent
- Death

The reason for taking a participant off study, and the date the participant was removed, must be documented in the case report form (CRF). In addition, the study team will ensure Off Treatment/Off Study information is updated in OnCore in accordance with DF/HCC policy REGIST-101. Lastly, the study team will ensure the participant's status is updated in OnCore in accordance with REGIST-OP-1.

## 5.11 Participant Replacement Strategy

Additional participants may be enrolled in a given Group to ensure that the required number of evaluable participants in each cohort is achieved. A participant that discontinues the trial for progressive disease or a drug-related AE will be counted in the intention to treat (ITT) population, defined as all randomized participants, but not be evaluable for the primary efficacy analysis in FAS population.

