# 5.4 Trial Blinding/Masking

Pre-operative treatment will be blinded; therefore, the treating investigator and subject will not know whether VB-111 or placebo is administered. An unblinded pharmacist or designee not involved in other study assessments will prepare the Pre-operative study drug of VB-111/Placebo. Post-operatively, treatment will be unblinded.

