## **11.2** Response Criteria for Target Lesions

**11.2.1** Complete response (CR:): All of the following criteria must be met:

- a) Complete disappearance of all enhancing measurable and non-measurable disease sustained for at least 4 weeks
- b) No new lesions
- c) Stable or improved non-enhancing (T2/FLAIR) lesions
- d) Participants must be off corticosteroids
- e) Stable or improved clinically

**11.2.2** Partial response (PR): All of the following criteria must be met:

- a) Greater than or equal to 50% decrease compared to baseline in the sum of products of perpendicular diameters of all measurable enhancing lesions sustained for at least 4 weeks
- b) No progression of non-measurable disease
- c) No new lesions
- d) Stable or improved non-enhancing (T2/FLAIR) lesions on same or lower dose of corticosteroids compared to baseline scan
- e) The corticosteroid dose at the time of the scan evaluation should be no greater than the dose at time of the baseline scan
- f) Stable or improved clinically
- **11.2.3** Stable disease (SD): All of the following criteria must be met:
  - a) Does not qualify for CR, PR, or progression
  - b) Stable non-enhancing (T2/FLAIR) lesions on same or lower dose of corticosteroids compared to baseline scan
  - c) Stable clinically
- **11.2.4** Progressive disease (PD): Any of the following criterion must be met:
  - a)  $\geq 25\%$  increase in the sum of products of perpendicular diameters of enhancing lesions compared to the smallest tumor measurement obtained either at baseline (if no decrease) or best response, on stable or increasing doses of corticosteroids
  - b) Significant increase in T2/FLAIR non-enhancing lesion on stable or increasing doses of corticosteroids compared to baseline scan or best response following initiation of therapy, not due to co-morbid events (e.g. radiation therapy, demyelination, ischemic injury, infection, seizures, post-operative changes, or other treatment effects)
  - c) Any new lesion

- d) Clear clinical deterioration not attributable to other causes apart from the tumor (e.g. seizures, medication side effects, complications of therapy, cerebrovascular events, infection, etc.) or changes in corticosteroid dose
- e) Failure to return for evaluation due to death or deteriorating condition
- f) Clear progression of non-measurable disease.

The RANO Response Criteria are summarized in Table 5.

Table 5: Summary of RANO Response Criteria.

	CR	PR	SD	PD#

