## **13.2** Definitions of Analysis Sets

- The Full Analysis Set (FAS) population will serve as the population for the analysis of primary efficacy endpoint TIL density in this study. The FAS population consists of all participants within each cohort who have received a preoperative dose of VB-111/placebo and had a surgery.
- The intention to treat (ITT) population is defined as all randomized participants. The ITT population will be used for secondary efficacy endpoints (PFS6, OS).
- The All Participants as Treated (APaT) population will be used for the analysis of safety data in this study. The APaT population consists of all allocated participants who received at least one dose of study treatment. At least one laboratory or vital sign measurement obtained subsequent to at least one dose of study treatment is required for inclusion in the analysis of each specific parameter. To assess change from baseline, a baseline measurement is also required.

A randomized, placebo controlled phase II, surgical trial to evaluate early immunologic pharmacodynamic parameters for the viral cancer therapy ofranergene obadenovec (VB-111) in patients with surgically accessible recurrent/progressive glioblastoma Version 3.0 February 18, 2021

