## **3.7.4 Unblinding**

The day after a participant's scheduled surgery, the Multi-Center Coordinating Center will email the participating site team to confirm participant's surgery. Once surgery has been confirmed, the Multi-Center Coordinating Center specialist will obtain the participant's randomization assignment from the 19-792 Unblinded Contact (or back-up) and will email the unblinded treatment assignment to the Participating Site Team. If patient is in Group C, the Participating Site Team will need to provide patient's SOC treatment plan as soon as possible. Once participant's adjuvant therapy is known (Group A or B)/confirmed (Group C), the Multi-Center Coordinating Center specialist will Register the participant centrally to his/her Step 2 Adjuvant Therapy and will email the Participating Site Team to confirm Step 2 Registration. **NOTE: Adjuvant treatment may not begin without** 

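### Section 5.11 removes participants who discontinue for progression or a drug-related AE from the primary analysis without limiting this to events before surgery, which read literally contradicts Sections 13.2 and 5.6

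*Combined protocol and SAP*

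**What the plan says.** Three sections of the combined protocol and SAP bear on who enters the primary comparison of TIL density.

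- **Section 5.11 (Participant Replacement Strategy):** "A participant that discontinues the trial for progressive disease or a drug-related AE will be counted in the intention to treat (ITT) population", "but not be evaluable for the primary efficacy analysis in FAS population". The sentence does not say whether the discontinuation must come before surgery.
- **Section 13.2 (Definitions of Analysis Sets):** "The FAS population consists of all participants within each cohort who have received a preoperative dose of VB-111/placebo and had a surgery". There are two conditions and no others. The same section makes the FAS the population for TIL density and defines ITT as everyone randomized.
- **Section 5.6 (Participant Evaluability):** a participant is unevaluable if the pre-operative dose could not be given, or if "a participant did not undergo the scheduled surgical resection for any reason, then the participant will be unevaluable for the primary efficacy analysis". It then adds: "Additional patients will be recruited to the trail until 15 evaluable patients in each arm".

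On timing, Sections 5.1 and 9.1 take the TIL sample from the protocol surgery. Section 5.4 says: "Post-operatively, treatment will be unblinded". Under Appendix B, Section 3.7.4, once surgery is confirmed the coordinating center "will email the unblinded treatment assignment to the Participating Site Team".

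**The concern.** The primary endpoint is fixed on the day of surgery, so a later discontinuation cannot make it missing. Read literally, 5.11 would still remove that participant from the primary analysis, and 5.6 would recruit a replacement. Membership of the primary analysis set would then depend on events that happen after randomization and after the endpoint is measured, and that are judged by staff who know the assignment.

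Those events need not be equally frequent across arms. VB-111-related AEs after surgery can occur only in Groups A and B, while progression and AEs related to standard-of-care drugs can also occur in Group C. Two analysts following different sections could build different primary analysis sets from the same trial.

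**Working it through.** **1. The sections side by side**

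| Participant | 13.2: in FAS? | 5.6: evaluable? | 5.11, literal |
|---|---|---|---|
| Dosed, stops for PD or drug-related AE before surgery, no surgery | No | No | Not evaluable |
| Dosed, operated on, later stops for PD or drug-related AE | Yes | Yes | Not evaluable |
| Dosed, operated on, later stops for another reason | Yes | Yes | Not addressed |

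The conflict is confined to the second row.

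**2. Can 5.11 be read as pre-surgery only?** Yes. PD criteria (d) and (e) in Section 11.2 need no post-operative scan; criterion (e) is "Failure to return for evaluation due to death or deteriorating condition". A drug-related AE can also follow the pre-operative dose. On the other hand, Section 11 takes the post-operative scan as the baseline for progression, so radiographic PD as the trial measures it arises after surgery. The wording permits both readings.

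**3. The plan's own figure.** Section 13.3 gives 84% power for 15 vs 30, a standardized difference of 0.8 and one-sided alpha of 0.05. The noncentral t calculation (43 df) gives 80.1%, and the normal approximation gives 81.2%. The 84% is not reproduced. That is a separate matter, and nothing below depends on it.

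**4. Enrolment under the literal rule.** Input: 15 evaluable per arm (5.6). Assumption: a fraction f excluded in every arm, since the documents give no rate. Total = 3 × ceil(15/(1 − f)).
- f = 0: 3 × 15 = 45
- f = 10%: 15/0.9 = 16.7, so 3 × 17 = 51
- f = 20%: 15/0.8 = 18.75, so 3 × 19 = 57

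**5. Type I error under the literal rule.** Each cell has 200,000 simulated null trials with normal data and a one-sided pooled t-test at 0.05 of A (15) against B+C (30). The test is unstratified, a simplification of the planned stratified test. A participant is excluded when a score with correlation ρ to TIL falls below its p-quantile, and is replaced until each arm has 15. The values of p and ρ are assumptions.

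| Excluded in A/B/C | ρ = −0.5 | −0.3 | 0 | 0.3 | 0.5 |
|---|---|---|---|---|---|
| 20/20/20% | 5.1% | 5.0% | 5.0% | 5.0% | 5.0% |
| 20/20/13.3% | 4.2% | 4.6% | 5.0% | 5.5% | 5.9% |
| 20/20/10% | 3.8% | 4.3% | 4.9% | 5.8% | 6.4% |

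A rerun with a different seed agreed to within about 0.2 points.

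**6. The same on the TIL scale.** The mean shift in an affected arm is ρ × φ(z_p)/(1 − p), in SD units. For p = 20% this is 0.280/0.8 = 0.350ρ; for p = 10% it is 0.1755/0.9 = 0.195ρ. With A and B at 20% and C at 10%, the shift in A minus B+C is (0.350 − 0.195)/2 × ρ = 0.0775ρ. At ρ = 0.3 that is 0.023 SD, or 0.012 TIL units at the plan's SD of 0.5. The design difference is 0.8 × 0.5 = 0.40.

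**The case against.** The best defence is that 5.11 was never meant to reach operated participants. Its heading concerns replacement, and it speaks of discontinuing the trial. Section 5.8 treats progression and unacceptable AEs as reasons to stop protocol therapy, after which follow-up continues, and Section 5.10 lists only loss to follow-up, withdrawal of consent and death as reasons to leave the study. An operated participant who stops VB-111 for progression has arguably not discontinued the trial. A pre-surgery reading also gives the sentence a function, since it states ITT status, which 5.6 does not mention. Finally, the FAS is defined only in 13.2, where a statistician would look first.

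Much of this stands, and it makes the pre-surgery reading the probable intention. It does not remove the conflict. Section 5.10 does not list progression or AEs as off-study reasons before surgery either, so discontinuing the trial is undefined at both times. The ITT status is already given by 13.2. And 13.2 is the natural source for the FAS without being stated to override 5.11.

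Three stronger readings are tempting and not supported:
- **Large distortion of type I error.** Setting exclusion in Group C to zero widens the range (2.6-8.3% at 20/20/0%, 3.5-6.6% at 10/10/0%). That is not realistic: progression occurs in Group C, its participants receive active drugs from Table 1, and the Appendix C coversheet records attribution to standard of care.
- **Enrolment of hundreds.** The historical PFS6 of 10% in Section 13.4 might suggest that 90% would be excluded, giving 15/0.10 = 150 per arm and 450 in all. PFS6 failures include deaths, and Section 11.4 allows treatment to continue past initial and, by exception, confirmed progression. A PFS6 failure is not the same as a trial discontinuation.
- **Loss of power.** Section 5.6 recruits to 15 evaluable per arm, so the cost is added enrolment.

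**Conclusion.** The point holds as a contradiction in the text. Followed literally, 5.11 excludes operated participants whom 13.2 and 5.6 include, and would discard valid primary-endpoint data because of later events observed unblinded. It should be fixed.

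Its size is modest and rests on assumptions. The documents give neither discontinuation rates nor any link between TIL density and these events, so the direction and size of any bias are unknown. Under modest assumed differences between arms, type I error moves from the nominal 5% to between 3.8% and 6.4%; with equal exclusion, or exclusion unrelated to TIL, it stays at about 5%. A reader might infer that the sponsor plans to exclude operated participants or that the primary test is already compromised. The documents support neither inference; they only leave the literal rule open.

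**What to change.** Replace the second sentence of Section 5.11 with:

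> A participant who, for any reason, does not receive the pre-operative dose or does not undergo the protocol surgery is counted in the ITT population but is not in the FAS, and will be replaced as stated in Section 5.6. Discontinuation of treatment or of the trial for any reason after surgery does not remove a participant from the FAS; Section 13.2 governs the FAS definition.

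This aligns 5.11 with 5.6 and 13.2 and settles precedence. It says that participants will be replaced because 5.6 makes recruitment to 15 evaluable per arm mandatory. The cost is one sentence in an amendment, with no additional patients or data and no change to clinical management. It should be made before any primary analysis set is built.
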